#### **Study Protocol**

##### Written Description of the Clinical Study

The study examined the efficacy of electrical-stimulation treatment at reducing disability status and improving mobility in persons with mild-to-moderate levels of disability due to multiple sclerosis (MS).

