##### Objective

The purpose of this study was to investigate the capacity of a 6-week treatment with neuromuscular electrical stimulation (NMES) to improve walking in individuals whose mobility has been compromised by multiple sclerosis.

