##### Design

In a double-blinded, randomized design, participants were assigned to one of two groups: narrow-pulse group ( $n = 13$ ;  $54.9 \pm 4.5$  yrs) or wide-pulse group ( $n = 14$ ;  $50.4 \pm 9.0$  yrs). Participants and evaluators were blinded to the type of intervention. Each participant attended 3 evaluation sessions and 18 NMES treatment sessions distributed over 6 wks. Each evaluation session comprised 2 days of testing.

Evaluation sessions were performed before (Week 0) beginning the 6-wk treatment, within 1 wk after finishing the treatment (Week 7), and approximately 4 wks after completing the treatment (Week 11).

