##### Methods

On the first day of the evaluation sessions, participants performed the two walking tests (25-ft walk and 6-min walk), a manual dexterity test (grooved pegboard), completed three questionnaires, and were instructed on how to measure daily levels of physical activity. Maximal walking speed was measured as the time it took to walk 25 ft as quickly as possible from a stationary start. The average of two trials was used as the measure of maximal walking speed. Walking endurance was characterized as the distance walked in 6-min around a 140-m track. Participants were encouraged to walk briskly, and the distance covered at 1, 2, 4, and 6 min was recorded.

The grooved pegboard test, the three questionnaires, and the daily levels of physical activity were used to assess disability status. Manual dexterity was quantified as the time taken to complete the grooved pegboard test, which required participants to place 25 pegs into holes on a pegboard as quickly as possible. The questionnaires were the Patient Determined Disease Steps (PDDS), Modified Fatigue Impact Scale (MFIS), and MS Walking Scale-12 (MSWS-12). Physical activity was measured with the GENEActive accelerometer (Activinsights Limited, Cambridge, UK) for 7 consecutive days beginning on the second day of evaluations and quantified during at least 24-hr days during that period.

Participants were asked to wear the waterproof sensors all the time, but were permitted to remove it at night if it disturbed their sleep. The monitor was worn on the same wrist and the data were sampled at 30 Hz. Custom software (Matlab R2015a, Mathworks, Natick, MA) was used to filter the signals (band pass of 0.2 to 15 Hz), calculate an average gravity-subtracted signal vector magnitude, quantify activity counts per second, and identify non-wear times ( $> 10$  hrs). Based on norms established for healthy adults, maximal activity category cut-points were set for *Sedentary* (1.4), *Light* (4.0), and *Moderate*

(11.3) accelerations per second to estimate the proportion of daily time spent performing different levels of physical activity. The main reason for including this assessment was to quantify the potential negative impact of the intervention on daily levels of physical activity.

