On the second day of the evaluation sessions, muscle strength and force steadiness were measured. Subjects lay in a supine position and a strap was placed around the forefoot and connected to a strain-gauge transducer (MLP-300, Transducer Techniques, Tenecula, CA). The measured force was sampled at 2 kHz (Power 1401, Cambridge Electronic Design, Cambridge, UK) and displayed on a monitor that was placed ~1 m in front of the subject. Muscle strength was quantified as the peak torque (N•m) achieved by the dorsiflexor and plantar flexor muscles of each leg when participants gradually increased muscle torque up to maximum and sustained it briefly. Participants performed up to 5 trials until two maximal values were within 10% of each other; the greater value was designated as the maximal voluntary contraction (MVC) torque. Participants then performed submaximal isometric contractions with the dorsiflexor and plantar flexor muscles to match target forces of 10% and 20% MVC torque with the self-reported less affected leg. The task was to match the target force displayed on the monitor and then maintain a steady contraction. The protocol comprised two 30-s trials at each target force with each muscle group. Force steadiness was measured as the coefficient of variation for force.

The NMES treatments were applied with an FDA-approved clinical device (Vectra Genisys Therapy System, DJO Global) that delivered symmetric, biphasic pulses of current through pairs of electrodes (2 x 3.5 in or 2 x 5 in each) placed on the skin overlying the muscles of each leg. NMES was applied to the dorsiflexor and plantar flexor muscles (10 min each muscle, 4-s on and 12-s off) of each leg. NMES was applied to one leg at a time in a counterbalanced order across sessions. Stimulus frequency was set at 100 Hz with a pulse width of 1 ms for wide-pulse stimulation and at 50 Hz with a pulse of 0.26 ms for narrow-pulse stimulation. To reduce the discomfort associated with NMES, the participant was encouraged to contract the involved muscles while the stimulation was being applied.

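### The aim is the efficacy of NMES itself, but both randomised groups receive active NMES, and no walking test or post-treatment evaluation is named primary

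*Protocol*

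**What the plan says.** **Aim.** The Written Description of the Clinical Study says that the study "examined the efficacy of electrical-stimulation treatment at reducing disability status and improving mobility". The Objective gives the purpose as to "investigate the capacity of a 6-week treatment with neuromuscular electrical stimulation (NMES) to improve walking". Neither sentence mentions pulse width or a comparison between two forms of stimulation.

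**Design.** "In a double-blinded, randomized design, participants were assigned to one of two groups": narrow-pulse (n = 13) and wide-pulse (n = 14). Under Methods, both groups are stimulated on the same muscles for the same time. The settings are 100 Hz "with a pulse width of 1 ms for wide-pulse stimulation and at 50 Hz with a pulse of 0.26 ms for narrow-pulse stimulation". No untreated or sham group appears.

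**Measures and timing.** On the first evaluation day, "participants performed the two walking tests (25-ft walk and 6-min walk". Separately, "The grooved pegboard test, the three questionnaires, and the daily levels of physical activity were used to assess disability status". Strength and force steadiness follow on the second day. After the Week 0 evaluation there are two more, "within 1 wk after finishing the treatment (Week 7), and approximately 4 wks after completing the treatment (Week 11". No measure or evaluation is called primary, main or secondary.

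**The concern.** The stated question and the randomised question are different. The aim asks about the effect of NMES; the allocation varies the type of NMES. If the two types work equally well, the randomised contrast is zero whether NMES helps a great deal or not at all. The question in the Objective must then be answered by comparing participants with their own Week 0 values, where randomisation and blinding to the type of stimulation give no protection. At stake is a claim that NMES improves walking carrying the authority of a double-blinded randomised design that did not test it.

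A second, smaller gap adds to this. Even if the aim is taken as walking alone, the protocol does not say which walking test, at which evaluation, was meant to carry the conclusion.

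**Working it through.** The protocol gives no alpha, effect size or sample-size calculation, so there is no stated figure to reproduce. The check has two parts.

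**1. What each comparison can estimate**

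For a given walking test, let *c* be the mean change from Week 0 that would have occurred without any stimulation effect. Let *e*W and *e*N be the effects of wide-pulse and narrow-pulse stimulation.

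- Expected change, wide-pulse group: *c* + *e*W
- Expected change, narrow-pulse group: *c* + *e*N
- Randomised contrast: (*c* + *e*W) − (*c* + *e*N) = *e*W − *e*N
- Pooled before-after change (14 and 13 of 27): *c* + (14/27)*e*W + (13/27)*e*N

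The randomised contrast removes *c* but says nothing about the size of *e*W or *e*N taken separately. The pooled change contains the effects but cannot separate them from *c*. A group without active stimulation would be needed to estimate *c*, and none is described.

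Methods gives concrete reasons not to take *c* as zero. Participants were encouraged to contract the muscles voluntarily during stimulation, did three passive stretching exercises, and attended 18 sessions performed or supervised by a physical therapist. The walking tests were also repeated at each evaluation. All of this is common to both groups, so it cancels in the contrast and remains in the before-after change.

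The two settings differ in frequency (100 versus 50 Hz) as well as pulse width (1 versus 0.26 ms). Wide-pulse versus narrow-pulse is thus a comparison of two combined settings.

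**2. How many results the protocol leaves open**

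Inputs from the protocol: 2 walking tests (Methods) and 2 post-treatment evaluations (Design), so 2 × 2 = 4 results.

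Assumptions not in the protocol: four separate tests of the randomised contrast, each two-sided at 0.05 (critical value 1.96), no true difference, and a common correlation ρ between the test statistics.

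For ρ = 0: 1 − 0.95⁴ = 1 − 0.8145 = 0.1855.

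For ρ > 0: 1 − ∫ φ(u) [Φ((1.96 − √ρ·u)/√(1−ρ)) − Φ((−1.96 − √ρ·u)/√(1−ρ))]⁴ du, by numerical integration.

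| ρ | Chance of at least one false positive, 4 results |
|---|---|
| 0 | 18.5% |
| 0.3 | 17.4% |
| 0.5 | 15.6% |
| 0.7 | 13.0% |

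One test at one evaluation, fixed in advance, would give the assumed 5%.

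**The case against.** **The design is openly described.** The protocol says plainly that both groups receive NMES and how the settings differ. It nowhere claims that the group contrast shows NMES efficacy. The capacity of a treatment to improve walking can be read as a before-after question, and a Week 0 evaluation is provided for it. This stands to the extent that nothing is hidden: a careful reader can work out what was randomised. It does not remove the mismatch, because a before-after reading is uncontrolled and the aim sentences do not say so.

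**The two aim statements do not contradict each other.** A reader might infer a conflict, since one covers disability status and mobility and the other only walking. The documents do not support that. Walking is part of mobility, one sentence is a summary and the other is headed as the objective. They differ in breadth, which is not a defect.

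**The analysis plan may fix the primary result.** It was not available for this review, and alpha, the decision rule and multiplicity handling may properly be there. So it cannot be said that no primary was ever chosen, only that this protocol does not designate one. The aim-design mismatch does not depend on the analysis plan, since no analysis creates a missing control group.

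**The error-rate range rests on assumptions.** This is right. One repeated-measures model could test both evaluations together. With two tests in place of four, the range is 8.3% to 9.8% at correlation 0.7 to 0. At correlation 0.8, four tests give 11.5%. Conversely, the walking questionnaire (MSWS-12), listed under disability status, could be counted as a third walking measure. A reader might infer that error was in fact inflated or results selected. Nothing in the protocol shows that; the figures describe only what is left open.

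**Conclusion.** The point holds in two parts of unequal weight.

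The main part follows from the design alone and needs no numerical assumption. Both aim statements concern NMES itself, while the randomised comparison can answer only wide-pulse versus narrow-pulse. Evidence that NMES improves walking is limited to change from Week 0 with no untreated or sham control, so it cannot by itself establish efficacy.

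The second part is that neither walking test and neither post-treatment evaluation is designated primary. The illustrative 13% to 18.5% depends on the assumed 0.05 level, the assumed correlations and four separate tests, and should not drive the weight given to the point. Because Design is in the past tense and reports the group sizes, naming a primary result now would not restore error control.

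**What to change.** 1. Restate the aim so that the randomised question is wide-pulse versus narrow-pulse NMES, with both settings identified by pulse width and frequency. Add that change from Week 0, within or across groups, is uncontrolled and cannot by itself establish NMES efficacy.
2. Before choosing anything, look for a dated record, including the analysis plan, that fixed the primary measure and evaluation. Report whatever it fixed, even if that is not a walking test.
3. If no such record exists, report both walking tests at both post-treatment evaluations with estimates and intervals. Label them, and any choice among them, post hoc and not confirmatory.

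The cost is a few sentences and a search of the files; no new data are needed. The downside is a narrower efficacy claim.

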##### Objective

The purpose of this study was to investigate the capacity of a 6-week treatment with neuromuscular electrical stimulation (NMES) to improve walking in individuals whose mobility has been compromised by multiple sclerosis.

##### Design

In a double-blinded, randomized design, participants were assigned to one of two groups: narrow-pulse group ( $n = 13$ ;  $54.9 \pm 4.5$  yrs) or wide-pulse group ( $n = 14$ ;  $50.4 \pm 9.0$  yrs). Participants and evaluators were blinded to the type of intervention. Each participant attended 3 evaluation sessions and 18 NMES treatment sessions distributed over 6 wks. Each evaluation session comprised 2 days of testing.

Evaluation sessions were performed before (Week 0) beginning the 6-wk treatment, within 1 wk after finishing the treatment (Week 7), and approximately 4 wks after completing the treatment (Week 11).

##### Methods

On the first day of the evaluation sessions, participants performed the two walking tests (25-ft walk and 6-min walk), a manual dexterity test (grooved pegboard), completed three questionnaires, and were instructed on how to measure daily levels of physical activity. Maximal walking speed was measured as the time it took to walk 25 ft as quickly as possible from a stationary start. The average of two trials was used as the measure of maximal walking speed. Walking endurance was characterized as the distance walked in 6-min around a 140-m track. Participants were encouraged to walk briskly, and the distance covered at 1, 2, 4, and 6 min was recorded.

The grooved pegboard test, the three questionnaires, and the daily levels of physical activity were used to assess disability status. Manual dexterity was quantified as the time taken to complete the grooved pegboard test, which required participants to place 25 pegs into holes on a pegboard as quickly as possible. The questionnaires were the Patient Determined Disease Steps (PDDS), Modified Fatigue Impact Scale (MFIS), and MS Walking Scale-12 (MSWS-12). Physical activity was measured with the GENEActive accelerometer (Activinsights Limited, Cambridge, UK) for 7 consecutive days beginning on the second day of evaluations and quantified during at least 24-hr days during that period.

Participants were asked to wear the waterproof sensors all the time, but were permitted to remove it at night if it disturbed their sleep. The monitor was worn on the same wrist and the data were sampled at 30 Hz. Custom software (Matlab R2015a, Mathworks, Natick, MA) was used to filter the signals (band pass of 0.2 to 15 Hz), calculate an average gravity-subtracted signal vector magnitude, quantify activity counts per second, and identify non-wear times ( $> 10$  hrs). Based on norms established for healthy adults, maximal activity category cut-points were set for *Sedentary* (1.4), *Light* (4.0), and *Moderate*

(11.3) accelerations per second to estimate the proportion of daily time spent performing different levels of physical activity. The main reason for including this assessment was to quantify the potential negative impact of the intervention on daily levels of physical activity.

On the second day of the evaluation sessions, muscle strength and force steadiness were measured. Subjects lay in a supine position and a strap was placed around the forefoot and connected to a strain-gauge transducer (MLP-300, Transducer Techniques, Tenecula, CA). The measured force was sampled at 2 kHz (Power 1401, Cambridge Electronic Design, Cambridge, UK) and displayed on a monitor that was placed ~1 m in front of the subject. Muscle strength was quantified as the peak torque (N•m) achieved by the dorsiflexor and plantar flexor muscles of each leg when participants gradually increased muscle torque up to maximum and sustained it briefly. Participants performed up to 5 trials until two maximal values were within 10% of each other; the greater value was designated as the maximal voluntary contraction (MVC) torque. Participants then performed submaximal isometric contractions with the dorsiflexor and plantar flexor muscles to match target forces of 10% and 20% MVC torque with the self-reported less affected leg. The task was to match the target force displayed on the monitor and then maintain a steady contraction. The protocol comprised two 30-s trials at each target force with each muscle group. Force steadiness was measured as the coefficient of variation for force.

The NMES treatments were applied with an FDA-approved clinical device (Vectra Genisys Therapy System, DJO Global) that delivered symmetric, biphasic pulses of current through pairs of electrodes (2 x 3.5 in or 2 x 5 in each) placed on the skin overlying the muscles of each leg. NMES was applied to the dorsiflexor and plantar flexor muscles (10 min each muscle, 4-s on and 12-s off) of each leg. NMES was applied to one leg at a time in a counterbalanced order across sessions. Stimulus frequency was set at 100 Hz with a pulse width of 1 ms for wide-pulse stimulation and at 50 Hz with a pulse of 0.26 ms for narrow-pulse stimulation. To reduce the discomfort associated with NMES, the participant was encouraged to contract the involved muscles while the stimulation was being applied.

The stimulation was applied while the participant was seated during the first and last two weeks (12 sessions) of the intervention and while standing in the middle two weeks (6 sessions). In the seated position, the legs were lifted parallel to the floor and the subject pushed against a restraint during application of NMES. In the standing position, subjects stood in a lunge position when NMES was applied to the plantar flexors and with the heels placed on a platform when the NMES was applied to the dorsiflexors. Current was progressively increased across sessions to the maximal tolerable level for each participant and then tapered during the last 3 sessions. After ~19 evoked contractions, the participant performed three passive stretching exercises with the involved leg muscles. The treatment sessions were performed or supervised by a physical therapist with clinical experience in providing such treatments. Each treatment session lasted ~50 min.

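### Does a 15 Hz upper filter edge on accelerometer data sampled at 30 Hz, followed by a gravity-subtracted magnitude, make the activity measure unworkable?

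*Protocol*

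**What the plan says.** The physical-activity paragraph in the protocol's Methods section gives the processing in two adjacent sentences. The first says that the monitor stayed on one wrist and that "the data were sampled at 30 Hz". The second says that custom Matlab software "was used to filter the signals (band pass of 0.2 to 15 Hz") and then went on to "calculate an average gravity-subtracted signal vector magnitude, quantify activity counts per second", and to identify non-wear time. Upper limits of 1.4 (Sedentary), 4.0 (Light) and 11.3 (Moderate) accelerations per second then divide the day into activity levels.

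The section does not give the filter type or order. It does not say whether the filter acts on the three axes or on the vector magnitude, by what operation gravity is removed, or how counts per second are formed from the samples.

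On the measure's role, the same section says: "The main reason for including this assessment was to quantify the potential negative impact of the intervention on daily levels of physical activity". The Objective concerns walking.

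**The concern.** Two things look wrong on a technical reading.

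- **Filter edge.** A digital band-pass normally needs its upper edge strictly below half the sampling rate. Here the two are equal, so a programmer who typed these figures into a standard design routine would get an error message.
- **Gravity.** Gravity is the constant part of the acceleration signal, and a 0.2 Hz lower edge applied to the axes removes it. If 1 g were then subtracted from the magnitude of the filtered axes, it would be taken from a signal that no longer contains it.

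The fixed cut-points are applied to whatever comes out of this chain, so the share of the day in each activity class depends on it. If rest were classed as vigorous movement, the study would lose its check on whether the intervention reduces daily activity.

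**Working it through.** **Inputs (Protocol, Methods):** sampling rate 30 Hz; band-pass edges 0.2 and 15 Hz; cut-points 1.4, 4.0 and 11.3 per second. The document derives no figure from these, so there is none to reproduce.

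**1. The edge against the Nyquist limit.** Nyquist = sampling rate / 2 = 30 / 2 = 15 Hz. Normalised edges = edge / Nyquist: 0.2 / 15 = 0.0133 and 15 / 15 = 1.0. Standard Butterworth and windowed FIR routines require a value below 1 and reject the upper edge. A frequency-domain band-pass with the same edges does run. The rejection is therefore a property of certain design routines, and the protocol names none.

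**2. What the edge would change.** Gain of a fourth-order Butterworth design at 30 Hz sampling (the type and order are assumptions made for this check):

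| Filter | 0.2 Hz | 1 Hz | 2 Hz | 5 Hz | 10 Hz |
|---|---|---|---|---|---|
| 0.2–14.99 Hz | 0.7071 | 1.0000 | 1.0000 | 1.0000 | 1.0000 |
| 0.2–14.9 Hz | 0.7071 | 1.0000 | 1.0000 | 1.0000 | 1.0000 |
| 0.2–14 Hz | 0.7071 | 1.0000 | 1.0000 | 1.0000 | 1.0000 |
| 0.2–12 Hz | 0.7071 | 1.0000 | 1.0000 | 1.0000 | 0.9956 |
| 0.2 Hz high-pass only | 0.7071 | 1.0000 | 1.0000 | 1.0000 | 1.0000 |

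Placing the edge just below 15 Hz, or dropping it, gives the same signal at these frequencies. Even 12 Hz costs only 1 − 0.9956 = 0.0044 of the amplitude at 10 Hz.

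**3. Aliasing.** Content at 16 to 20 Hz folds to 30 − 16 = 14 Hz down to 30 − 20 = 10 Hz. That follows from sampling at 30 Hz and would happen with any digital upper edge. It is no argument against the one written.

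**4. Gravity, for a motionless sensor.** The simulation used 1 g on one axis plus noise of 0.005 g per axis, with a 0.2–14.9 Hz filter.

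- Gravity removed once:
  - 1 g taken from the unfiltered magnitude: mean absolute value 0.0039, or 0.0039 × 30 = 0.12 summed per second.
  - Filter applied to the magnitude: also 0.0039, or 0.12.
  - Filter applied to the axes, then the magnitude taken: 0.0078, or 0.0078 × 30 = 0.23.
  - All three lie far below the Sedentary limit of 1.4.
- Gravity removed twice (axes filtered, then 1 g subtracted): signed mean 0.0078 − 1 = −0.9922. The class then depends on how the count is formed:
  - absolute value summed over 30 samples: 0.9922 × 30 = 29.8, above 11.3;
  - absolute value averaged: 0.99, below 1.4;
  - signed mean: −0.99;
  - negative values set to zero: 0.

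Misclassified rest therefore needs three things together: a second subtraction, an absolute value, and a sum over samples. The protocol states none of them, and for the vector magnitude it says average.

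**The case for a change.** The strongest reply is that a reader cannot tell which of the two frequencies is misstated, and that an error in the sampling rate would not be harmless. If counts are summed over the samples in each second, they scale with that rate. For a simulated 0.1 g movement at 2 Hz on two axes, the sum of |magnitude − 1 g| is 1.9 per second at 30 Hz. That is about 1.9 / 30 = 0.063 per sample, hence 0.063 × 60 = 3.8 at 60 Hz and 0.063 × 100 = 6.3 at 100 Hz. Against the cut-points these are Light, Light and Moderate, so identical movement could change class. The two valid ways of removing gravity also differ: the same movement gives 1.9 or 2.7, and 2.7 / 1.9 = 1.42, about 40% apart though both Light.

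The arithmetic stands, but it does not show an error. Nothing in the document suggests that the rate was other than 30 Hz, and the 60 and 100 Hz figures are hypothetical. The scaling disappears if counts are averaged over samples. The cut-points come from norms whose derivation the protocol does not give, so their fit to this chain cannot be judged from the text. What remains is that the description is too thin for an outsider to rebuild the code exactly. That is missing detail in a methods paragraph. The analysts hold that detail, because the text reports in the past tense processing that was done with existing software.

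**Conclusion.** No change follows. The coincidence of 15 Hz with the Nyquist limit is real, and as a description of a digital band-pass it is slightly careless. Read sensibly, it describes a 0.2 Hz high-pass, and restating the edge would leave the signal at 1 to 10 Hz unchanged to four decimals. Double removal of gravity is an inference from the order of words. The ordinary reading, in which the gravity-subtracted magnitude is the result of a single removal step, is coherent and classes a still sensor as Sedentary.

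This rests on two assumptions: that the data were sampled at 30 Hz as written, and that the software removed gravity once. The document contradicts neither. A re-run of the three evaluations would be warranted only if the code were found to depart from a valid chain, and nothing here shows that. The protocol describes one chain for all the activity data, and that measure supports a study whose objective is walking.

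### Do the arm names, narrow pulse and wide pulse, hide a second difference in stimulus frequency that undermines the randomised comparison?

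*Protocol*

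**What the plan says.** The Design section names the arms by one attribute: "participants were assigned to one of two groups: narrow-pulse group" (n = 13) or wide-pulse group (n = 14).

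The Methods section gives the settings behind the names: "Stimulus frequency was set at 100 Hz with a pulse width of 1 ms for wide-pulse stimulation and at 50 Hz" for the other arm, whose settings read in full "at 50 Hz with a pulse of 0.26 ms for narrow-pulse stimulation". The treatment time and duty cycle, "10 min each muscle, 4-s on and 12-s off", are given without distinction by arm.

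Current follows a single rule that does not mention the arm: "Current was progressively increased across sessions to the maximal tolerable level for each participant and then tapered during the last 3 sessions". No achieved currents are given.

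The Objective section says the purpose was to "investigate the capacity of a 6-week treatment with neuromuscular electrical stimulation (NMES) to improve walking". It does not mention pulse width or frequency.

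**The concern.** The wide-versus-narrow comparison is the only randomised contrast in the trial. The names invite the reader to treat pulse width as the factor under test, yet frequency doubles along with it. No arm combines 100 Hz with 0.26 ms, or 50 Hz with 1 ms. Current is also titrated to individual tolerance, and tolerance could depend on both settings.

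If the result were reported as a pulse-width effect, a difference could in truth be due partly or wholly to frequency. A null result could be read as evidence that pulse width is unimportant, when the design cannot show that. Covariate adjustment in a later analysis plan could not repair either reading.

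**Working it through.** **Inputs** (Protocol, Design and Methods): wide-pulse arm 100 Hz and 1 ms; narrow-pulse arm 50 Hz and 0.26 ms; 10 min per muscle; 4 s on and 12 s off; about 19 evoked contractions before stretching. The protocol states no figure for the contrast between arms, so there is none to reproduce.

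**1. Size of each difference.**
- Frequency ratio: 100/50 = 2.0.
- Pulse-width ratio: 1/0.26 = 3.85.
- Pulse time per second of stimulation (frequency × width): 100 × 1 = 100 ms against 50 × 0.26 = 13 ms. The ratio is 100/13 = 7.69 = 2.0 × 3.85.
- Share of that ratio due to frequency, on the log scale: ln 2 / ln 7.69 = 0.34. The other 0.66 comes from width.

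**2. Pulses delivered per muscle.** One cycle lasts 4 + 12 = 16 s, so 10 min holds 600/16 = 37.5 cycles. Half of that is 18.75, which agrees with the protocol's figure of about 19 contractions. Pulses per muscle: 37.5 × 4 × 100 = 15,000 against 37.5 × 4 × 50 = 7,500.

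**3. Aliasing.** Let T = 1 for wide pulse and 0 for narrow pulse. Then frequency = 50 + 50T and width = 0.26 + 0.74T. Each is an exact linear function of T, and so of the other. A model with an intercept and both settings has three columns but rank 2. Only the effect of T, meaning the whole regimen, can be estimated.

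**4. Current.** Charge per second is proportional to current × frequency × width, so the wide-to-narrow ratio is 7.69 × r, where r is the wide-to-narrow ratio of achieved current. The protocol does not give r. For assumed values:

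| Assumed r | Ratio of charge per second |
|---|---|
| 1 | 7.69 |
| 0.5 | 3.85 |
| 0.25 | 1.92 |
| 0.13 | 1.00 |

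The 7.69 therefore describes the programmed settings at equal current. It is not the contrast that participants received.

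**5. Names against definitions.** The Design section uses the short names. The Methods section defines each name by a frequency and a width in one sentence. The two places do not contradict each other: one abbreviates what the other specifies. Neither the Objective nor the opening description of the study claims anything about pulse width as such.

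**The case for a change.** The best argument for acting is that aliasing is a property of the design and no analysis plan can undo it. A factor that doubles the pulse count is not a trivial companion to pulse width, the names omit it, and the contrast is the only randomised one. Rewording the names, limiting the conclusion and tabulating current by arm would cost almost nothing.

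The arithmetic and the aliasing stand in full. Three parts of the argument do not carry through to a change:

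- **Current is not a second designed difference.** All participants follow one titration rule. If achieved current differed by arm, that would be a consequence of the assigned settings after randomisation, and so part of the regimen being compared.
- **Attribution to pulse width is inferred from the names.** No hypothesis or conclusion in the protocol makes it. Separating the two settings would need further arms, to answer a mechanistic question that the protocol does not ask.
- **The harm would arise in a report.** How a difference is worded, and whether achieved current is tabulated, are matters commonly settled in an analysis plan or report. The analysis plan is not at hand here.

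An opposing-effects explanation of a null result is possible in principle, but nothing in the protocol supports it.

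**Conclusion.** No change to the plan is needed. The two settings are fully aliased (2.0-fold in frequency, 3.85-fold in width), so a group difference can be credited only to the combined regimens. The protocol discloses both settings for each arm and makes no narrower claim. Random assignment to two specified regimens gives a valid comparison of those regimens. Relabelling would change no stimulation setting, analysis, estimate or error rate.

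This rests on two assumptions: that the results are read as a comparison of regimens, as the Methods definitions imply, and that current was titrated by the same rule in both arms, as written. A careful analyst would describe the contrast as 1 ms at 100 Hz against 0.26 ms at 50 Hz, claim no effect of either setting alone, and summarise achieved current by arm. That is a wording clarification and is optional. Whether two active arms can answer the broader question about electrical stimulation is a separate matter, not judged here.
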